1.1 RATIONALE

Chronic obstructive pulmonary disease (COPD) is one of the major disorders included in the WHO program addressing non-communicable diseases. It is currently the third leading cause of death. Despite COPD prevalence is not expected to increase in developed countries, projections for the next decade indicate an escalating burden of this condition on both health and social support systems, mainly due to population ageing.

Prevention of acute episodes (exacerbations) in patients with COPD¹, as well as enhanced management of comorbidities², are the two major actionable factors to reduce the societal burden of the disorder.

The 2023 GOLD guidelines¹ for COPD management states that *"exacerbations are mainly triggered by respiratory viral infections although bacterial infections and environmental factors such as ambient air pollution and temperature changes may also initiate, or amplify, these events"*.

The current protocol has been primarily designed to assess the impact of altered indoor air quality (IAQ) on acute events (exacerbations) in patients with COPD showing comorbidities assessed by Adjusted Morbidity Groups (GMA)^{3,4} scoring.

The follow-up of a cohort of 200 vulnerable patients over a period of three years offers a unique opportunity to explore the potential of digitally supported integrated care services for enhanced management of chronic patients. To this end, the current observational study protocol aims to assess the impact on patients' empowerment for self-management, as well as potential healthcare efficiencies generated by a nurse case manager supporting the relationships between patients and their primary care physicians.

The study design also allows to capture a variety of patients' self-reported data that, in turn, should facilitate detection of subclinical events eventually related with impaired IAQ. Consequently, there are clear synergies between the two goals addressed in the protocol.

1.2 OBJECTIVES

***** *Project objectives:*

Analyse the relationships between patient's home IAQ and health status with focus on acute health effects.

Local research group objectives:

> To assess the potential of digitally enabled integrated care for community-based preventive management of exacerbations.

To explore enhanced assessment of lung function at community level by combining measurements of forced oscillation technique (FOT) and forced spirometry (FS).

***** The results of this study will be also used to:

Provide the information needed to design in vivo or in vitro studies facilitating the identification of sources, health impact, and mechanisms of action that ultimately should enable the generation of recommendations for the prevention of undesirable health effects of impaired IAQ (PHASE II, > M18).

1.3 METHODS

1.3.1 Study Population (n=200)

The pilot will be entirely developed in the Integrated Healthcare District of Barcelona-Esquerra (AISBE) (surface of 74,668 m^2 and with 520 k citizens).

From AISBE, **200** multimorbid outpatients with chronic obstructive pulmonary disorders (COPD, bronchiectasis, and severe asthma refractory to therapy) will be recruited for the study. The study will be focused on moderate to high-risk outpatients identified through the AMG score, among them, the patients with cardiovascular disorders and type II diabetes mellitus will be prioritized.

As described in detail below (**1.3.1.1**), a first candidate screening will be made through the Catalan Health Surveillance System⁵ (CHSS), identifying all the potential candidates that meet the conditions exposed above.

As part of the RAE consulting sessions, the research protocol will be explained to primary care professionals and the role of the nurse attached to the project, who will join the primary care team (CAPSBE and Numància) as case manager nurse. This nurse will contact, on behalf of the primary care team, the candidates and inform them about the study within a rutinary follow up visit If the candidate manifests the willingness to participate, the study nurse to provide him sufficient information to judge whether or not participating in the study, as well as clarifying any question that may arise Before being enrolled in the study the participants must sign an informed consent.

✓ The AMG is the risk assessment tool used in Spain to generate, and update, population-based risk stratification pyramids at regional level.

✓ It is based on number of morbid conditions (multimorbidity), complexity and impact of those conditions on the healthcare system

✓ It is updated every six or twelve months for health policy purposes. But it is also increasingly used for clinical purposes.

✓ The high potential of the AMG has been recognized by WHO and it has been included as one of the core features being transferred to different EU regions within the Joint Action JADECARE (2020-23) https://www.jadecare.eu/

1.3.1.1 The elaboration of the study dataset & the patients' enrolment procedure

Preparation of the study cohort

Due to the uniqueness of the process adopted in the current study protocol, the generation of a pre-study database is deemed necessary to perform a detailed screening of potential participants. The rationale of the process for generation of the pre-study dataset relies on three considerations indicated below. The approach will be constrained to the development of the Barcelona pilot of the K-Health in Air project.

- a) Safe access to the CHSS dataset owned by CatSalut Since January 2021, key personnel of the research team (IDIBAPS and CatSalut-DS3) has been collaborating with the OECD Action to Support JADECARE (https://www.jadecare.eu/) under HaDEA (https://hadea.ec.europa.eu/) supervision. The IP of the current research is the coordinator of the Catalan original Good Practice in JADECARE. This ongoing collaboration allows a safe extraction of a dataset of approximately 40 thousand including all patients with chronic obstructive disorders living in the AISBE district. Data on diagnoses, GMA scoring and use of health and social care resources are available. High-quality standards for data management ensuring patients' privacy have been well established. Data management will be conducted by [name] ([name], IDIBAPS) in collaboration with [name] (EV, CatSalut-DS3).
- b) Secure merging of the CHSS dataset with the corresponding Electronic Health Records at Hospital Clinic - The main purpose is to validate the diagnosis of chronic obstructive pulmonary disease and assess disease severity. Accordingly, the two main inclusion criteria (Section 1.3.1.2), GMA scoring and severity of respiratory condition, will be properly evaluated. Such merging will be done, within the Hospital Clinic premises, by [name] in collaboration with the Clinical Informatics team (Dr [name]) keeping identical standards of quality for data management.
- c) High quality and potential of the final dataset. The elaboration of the list of potential candidates for the study, as described, is limiting potential selection bias to the following two factors: i) willingness to participate, and ii) level of digital literacy. We believe that the approach can facilitate generalization of the results of the clinical management protocol. Moreover, it offers clear logistics advantages for the recruitment of candidates while following good practice for clinical research.

The database created through this process will strictly serve the intended purpose and will not be utilized for any other purposes or studies.

Enrolment of candidates

Step 1 - Engagement of primary care professionals - The elaboration of the dataset of potential candidates will allow the identification of the corresponding primary care physicians. The study protocol will be initially constrained, within AISBE, to the primary care units pertaining to CAPSBE and Numancia. Several sessions, aiming at engaging the primary care physicians into the study, are planned. Full information on the IAQ protocol will be provided and share care agreements between primary care and specialists ([name], with the support of the home hospitalization team and the pneumology service) will be proposed. The nurse case manager ([name]) will have two main roles in the study: i) collection of information for the IAQ study protocol, and ii) ensure care continuum. Main actions of the nurse case manager will be: i) promotion of patient's empowerment for self-management/early detection of exacerbations, and ii) bridging between primary care teams and specialized care.

Step 2 - Initial contact with potential candidates – An initial phone visit of the nurse case manager on behalf of the primary care team will be used to: i) introduce the project, ii) do a short screening of the potential candidate assessing inclusion/exclusion criteria, and, if the patient agrees, iii) set the first face-to-face visit at patient's home.

Step 3 – Recruitment and characterization of the candidates - We plan three, face to face visits of the nurse case manager at the patients' home to complete the process of recruitment and characterization of each patient.

Visit 1 - Detailed information on the study protocol and signature of the consent form *(estimated 30-45 min)*

Visit 2 - Clinical assessment and agreement on the clinical support plan, to be shared with the primary care physician, and patient's education for self-management mimicking the protocol recently reported in ⁶. Instructions for use of the chat and sensors (home-based IAQ sensor and wrist sensor) (estimated 60-90 min)

Visit 3 – Administration of the K-Health in Air questionnaires for baseline characterization and pulmonary capacity assessment through FS and FOT measurements *(estimated 45 minutes).*

At the end of visit 3, the patient will be fully recruited and characterized. The follow-up plan will be guided by the IAQ study protocol described below, but the clinical management of the patients will be personalized according to the individual share care plan agreed with the patient and their primary care physician. The communication channel (chat) managed by the nurse case manager will have a central role in the decision-making process. A close follow-up of the evolution of the clinical setting with be done with the supporting role of the PI ([name]). The information provided by the wrist sensor will not be used to take clinical decisions by the nurse case manager. The use of the data provided by the wrist sensor is described in detail below.

1.3.1.2 Inclusion criteria

- ✓ Patients must be allocated in the moderate, high, and very high-risk tiers of the populationbased risk pyramid deducted from the AMG score distribution of the entire region of Catalonia.
- ✓ Patients must have at least a chronic obstructive pulmonary disease (COPD, bronchiectasis, or severe asthma). Clustering of COPD, cardiovascular disorders and diabetes type II will be prioritized.
- ✓ Patients must be able to participate throughout the entire study period (3 years).
- ✓ Patients must be autonomous for their daily life activities.
- ✓ Patients must sign the informed consent for secondary use of the data collected.
- ✓ The patients must have the commitment to wear a wrist sensor during the entire study period.
- ✓ The patients must live in AISBE health district.

1.3.1.3 Exclusion criteria

- × Patients with dementia and/or unable for follow-up purposes/unable for independent daily life activities will not be considered for the study.
- × Patients with Wi-Fi internet connection available at home will be prioritized, but it will not be an exclusion criterion, in these cases the connection might be granted through GSM-SIM.
- × Patients with a smartphone and acceptable skills for digital tools management will be

prioritized, but it will not be an exclusion criterion. To guarantee the inclusivity of the protocol, the study also considers the participation of patients who might have limitations in using digital technologies. In this regard, three participation modes based on the patients' digital skills and resources are proposed:

Basic participation (Minimum requirement to participate in the study): implies the collection of fundamental data along with a subsequent telephonic follow-up for patient management.

Intermediate participation: In addition to the basic modality, this level involves the use of a wrist sensor to monitor physical activity, heart rate and derived variables (Requires a smartphone - Passive data collection).

Complete participation: In addition to the intermediate modality, this level considers using a digital application (App) for the patient's follow-up and management (Requires a smartphone and digital literacy).

Detailed information on the implications for the study can be found in the section 1.3.3.4 "Modes of participation." This section elucidates the specific data collection methods employed within each participation mode.

1.3.2 Study period

July 2023 – March 2026. The recruitment of participants will be initiated on early July 2023 and completed within two-months. The follow-up will last until March 2026, and a first assessment of the results will be done at M18 (February 2024).

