1.4.1.2 Health Circuit - Data management

K-HEALTHinAIR study protocols in Barcelona consider the use of a digital health tool for the followup of study participants.

The digital health tool will be provided by the spin-off **Health Circuit SL** (www.healthcircuit.es), with a prototype-level digital health platform hosted in a private cloud in European servers that will be released in April 2023 for the inclusion of the first study participants.

Study participants will be registered in the Health Circuit platform by the nurse case manager at study entry using a project email account ([contact]). The patient's study ID will be set as username, and the password will be defined by the patient at this moment. Patient identifiers, either direct or indirect, will not be used to define the patient user, nor will they be collected at any time through the Health Circuit application.

Figure 1 depicts the data management flow chart of the Health Circuit application. After the inclusion of a study participant, the research protocol will dictate the release of monitoring tasks to study participants. Monitoring tasks will include regular follow-up questionnaires, PROMs/PREMs using Likert scales and monitoring of daily physical activity (steps and minutes of moderate/vigorous physical activity), stress, heart rate variability (HRV) and sleep patterns that will be monitored by the Beat One watch. In addition, study participants will be able to communicate with the nurse case manager with an off-line chat. The communication channel is expected to be key in keeping the study participant adherent to the research protocol. **The data collected through Health Circuit will be periodically imported by the nurse case manager to a dedicated REDCap project at https://redcap.clinic.cat.**

Backend for health Professionals Figure 1: Data acquisition flow diagram of the Health Circuit application.

From the Health Circuit App in the smartphone of the study participant to the Health Circuit servers hosting the research protocol, the following information will be exchanged. The exchange of data

with the APP is always carried out using only the patient study ID). The data will not be shared with any other entity unless there is a legal obligation of a competent body.

The APP data is stored in three independent databases:

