1.5 EXPECTED OUTCOMES AND CLINICAL IMPACT

- Study of the relationships between patient's home IAQ and health status with focus on acute health effects.

The analyses will be done considering two different levels: i) Barcelona pilot, and ii) information obtained at consortium level (using data from different scenarios). The methodological approach proposed by the project EU-Stands4PM: Standards for In Silico Models for Personalized Medicine (https://www.eu-stands4pm.eu/) will be adopted in the current project. Briefly, EU-Stands4PM combines data driven analyses and knowledge-based approaches to address the target objective.

The main expected outcome is the identification of IAQ-related factors with potential deleterious impact on health status. Subsequent studies to be planned in PHASE II (\geq M18) may help to analyse causality and identify thresholds for specific pollutants.

- Identifying factors triggering exacerbations in high-risk patients with respiratory diseases.

The study design, including continuous patients' monitoring with the wrist sensor (One Beat) and registry of incidences using the chat, as well as continuous IAQ monitoring (MICA-INBIOT), should allow early identification of acute clinical episodes facilitating: i) the identification of factors triggering exacerbations and, specifically, the role of IAQ, and ii) early management of exacerbations preventing progression and subsequent need for emergency room visits and/or hospitalizations.

- Assessing the potential of digitally enabled integrated care for community-based preventive management of exacerbations.

Previous studies^{10,11} and recent pilot data support the hypothesis that digital support of integrated care services for preventive management of chronic respiratory patients with co-morbidities generates healthcare efficiencies by enhancing patients' empowerment for self-management and reducing the use of healthcare resources, mainly emergency room visits and hospitalizations. Both incidences and health outcomes, after one year, will be assessed in comparison with a control group generated using propensity score matching techniques.

- Exploring enhanced assessment of lung function at community level by combining measurements of FOT and FS.

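### Do the study dates contradict the three-year follow-up and the M18 label on the first assessment?

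*Protocol*

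**What the plan says.** Protocol Section 1.3.2 sets the study period as July 2023 to March 2026. On entry it says: "The recruitment of participants will be initiated on early July 2023 and completed within two-months". On the end of follow-up and the first look at results it says: "The follow-up will last until March 2026, and a first assessment of the results will be done at M18 (February 2024".

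Two other places give a length in years. The rationale (Section 1.1) says: "The follow-up of a cohort of 200 vulnerable patients over a period of three years offers a unique opportunity". The inclusion criteria (Section 1.3.1.2) say: "Patients must be able to participate throughout the entire study period (3 years". A further criterion in that list uses the same period without giving a length: "The patients must have the commitment to wear a wrist sensor during the entire study period".

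The label M18 also marks the start of Phase II, with no date, in Section 1.2 ("undesirable health effects of impaired IAQ (PHASE II, > M18") and in Section 1.5, in the sentence that begins "Subsequent studies to be planned in PHASE II". Table 7 (Section 1.3.3.3) has columns Entry and M1 to M12, which are months since entry, for the first year only. Section 1.3.3.2, item G, mentions the eighteenth month and states that it is counted on follow-up.

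**The concern.** An eligibility criterion should not ask for a period that the study's own dates cannot deliver, and on the printed dates no patient can complete 36 months. If a main analysis used three-year outcomes, that shortfall would matter.

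The M18 label raises a second doubt. A reader who takes M as months since entry, as in Table 7, would expect month 18 in early 2025, not February 2024. If February 2024 is right, the first assessment comes before anyone has a full year of follow-up. If the year is a slip, it comes about a year later. The Phase II markers in Sections 1.2 and 1.5 carry no date, so they inherit the ambiguity.

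**Working it through.** **Inputs** (all from Section 1.3.2 unless noted)
- First entry: taken as 1 July 2023 (early July).
- Last entry: taken as 1 September 2023 (two months later).
- End of follow-up: 1 to 31 March 2026, since only the month is given.
- First assessment: 1 to 29 February 2024.
- Stated length: 36 months (Sections 1.1 and 1.3.1.2).

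Formula: months = days / 30.4375.

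**Follow-up per patient**

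| Entry | End | Days | Months | Short of 36 |
|---|---|---|---|---|
| 1 Jul 2023 | 1 Mar 2026 | 974 | 32.0 | 4.0 |
| 1 Jul 2023 | 31 Mar 2026 | 1004 | 33.0 | 3.0 |
| 1 Sep 2023 | 1 Mar 2026 | 912 | 30.0 | 6.0 |
| 1 Sep 2023 | 31 Mar 2026 | 942 | 30.9 | 5.1 |

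The 36-month figure cannot be reproduced. The range is 30 to 33 months (2.5 to 2.75 years), and the shortfall is 3/36 = 8% to 6/36 = 17%. Thirty-six months from entry would end between July and September 2026.

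**Where February 2024 falls after entry**
- First entrants: 215/30.4375 = 7.1 to 243/30.4375 = 8.0 months.
- Last entrants: 153/30.4375 = 5.0 to 181/30.4375 = 5.9 months.

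February 2024 is therefore about month 5 to 8 on the entry clock.

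**Which clock makes M18 equal February 2024?**
- Counting back 18 months puts month 0 in August 2022. If the first month is numbered 1, it is September 2022. Both precede recruitment by about 10 to 11 months, so this can only be a project clock.
- Counting forward from entry, month 18 is January 2025 for the first entrants and March 2025 for the last. The gap from the printed date runs from 307 days (29 February 2024 to 1 January 2025, 10.1 months) to 394 days (1 February 2024 to 1 March 2025, 12.9 months), or about 10 to 13 months.

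**What depends on these figures?**
- The matched-control comparison in Section 1.5 is made after one year. Month 12 falls between July and September 2024, well inside follow-up.
- Lung function is measured every 6 months. Month 30 is the last such point the latest entrants reach: 1 September 2023 plus 30 months is 1 March 2026.
- Table 7 stops at M12 and has no M18 column, so it contradicts nothing in Section 1.3.2. It only shows the letter M used for months since entry.
- The wrist-sensor criterion states no length, so it overstates none.
- No analysis is set at 36 months, and none is tied to M18.

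**The case for a change.** The strongest case for acting is that the three years stand inside an eligibility criterion, where they gloss the study period and are not loose narrative. Someone applying the list literally could turn away a patient able to take part until March 2026 but not until mid-2026. In addition, the text does not settle whether M18 rests on an unstated project calendar or on a wrong year: 18 months from August 2023 is February 2025.

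Part of this stands. The duration is misstated, and the text at hand does not define the month count. The practical force is small, however. The working part of the criterion is the whole study period, and Section 1.3.2 gives its start and end. The error also runs in the harmless direction, since a patient able to commit for three years can certainly commit for 30 to 33 months. The protocol gives no figure for patients who might fall between the two lengths; that they are few is a judgement.

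On M18, the authors say so when they mean follow-up time (Section 1.3.3.2, item G). The bare label appears only as a phase marker and beside a printed date, which is how a project month is normally used. Section 1.3.3 also refers to a General Project Description that is not at hand and may define it. Section 1.3.2 promises only a first assessment of results. It does not say that this includes the one-year comparison, so holding it before month 12 contradicts nothing.

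**Conclusion.** The arithmetic behind the concern is right: 30 to 33 months against a stated 36, and a first assessment about 5 to 8 months after entry under an M18 label. No change to the plan follows. The first point is a rounded duration alongside explicit dates. The second is an abbreviation whose likely origin, a project calendar starting around August or September 2022, reconciles label and date. Correcting either would alter wording only; no visit, sample size, analysis or result would move.

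This rests on three assumptions: recruitment ran from early July to about early September 2023 as planned, the printed March 2026 and February 2024 dates are the intended ones, and no analysis specified elsewhere needs 36 months of follow-up. If February 2024 were itself a slip for 2025, the first assessment would come a year later, but nothing in the protocol hangs on that date.
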